Check *each* word correctly recalled. Total equals words *not correctly* recalled.

a. Number of errors (range = 0-2)

b. Time at completion or second error
(maximum = 240 seconds total)

		
----------------------	----------------------	----------------------

If task not administered, please specify reason (check one):

- Not done (for reasons other than physical/cognitive impairment)
- Subject refused
- Subject unable for physical reasons
- Subject unable for cognitive reasons (If selected, enter a score of "5" in eCRF)

Scoring: (circle one)

0	= 0-30 seconds at completion or second error
1	= 31-60 seconds at completion or second error
2	= 61-90 seconds at completion or second error
3	= 91-120 seconds at completion or second error
4	= 121 - 239 seconds at completion or second error
5	= 240 seconds at completion or second error

14. Number Cancellation

Place the practice form face up in front of the participant. Say the following instructions word-for-word: "On the top of this page are two numbers. In this row of numbers you will find these numbers mixed in with other numbers. I'd like you to begin here" (point to the beginning of the line) and cross off each number that matches either of the two numbers at the top of the page. Please work as quickly as you can." Correct any errors and re-explain as necessary to ensure understanding of the task. Discontinue the example after 30 seconds or when the participant finishes the line, whichever is first.

Place the test form face up in front of the participant. Say the following instructions word-for-word: "On the top of this page are two numbers. Throughout this page you will find these numbers mixed in with other numbers. I'd like you to begin here" (point to the beginning of the line) and going across off each number that matches either of the two numbers at the top of the page. Please work as quickly as you can."

If the participant stops at the end of a line, before the last line, and there is still time left, ask him or her to "keep going." Discontinue the task after 45 seconds or when the participant finishes the last line, whichever is first.

a. Number of targets hit (range = 0-49)

--	--

b. Number of errors

--	--

c. Number of times reminded of task

--	--

[figure not shown]
If task not administered, please specify reason (check one):

- Not done (for reasons other than physical/cognitive impairment)
- Subject refused

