Prior and concomitant medications will be tabulated for the ITT population by WHODDE ATC level 2 classifications, preferred term, and treatment. If a subject reports the same preferred term multiple times, then the frequency of that preferred term will only be incremented by one. As with the preferred term, if a subject reports multiple medications within the same ATC level 2 classification, then the frequency of that ATC level 2 classification will only be incremented by one. Percentages will be calculated using the total number of subjects in the safety population. Each summary will be ordered by descending order of incidence of preferred term within each ATC class. Prior and concomitant medications will be included in a data listing.

4.6.5. *Treatment Compliance*

Not applicable.

4.7. *Efficacy Analyses*

The primary efficacy hypothesis test will be performed using a 5% significance level. For the secondary efficacy endpoints, hypothesis tests will be performed individually at the 5% significance level. All hypothesis tests will be performed with two-sided alternative hypotheses. No adjustments on the significance level for multiple comparisons are planned, as this is a phase 1/2 study. All efficacy analyses will be based on the ITT population.

4.7.1. *Primary Efficacy Analysis*

The primary objective of this study is to test the hypothesis that AstroStem is superior to placebo in the improvement on neurological/neurocognitive assessment from baseline to week 30 in patients with Alzheimer's Disease.

The primary analysis will evaluate the efficacy of AstroStem compared with placebo on the overall mean change from baseline to week 30 in ADAS-Cog score. The primary efficacy variable will be summarized with means, standard deviations, medians and ranges, overall and by group. The change from Baseline ADAS-Cog score will be analyzed with Student's t-test or Kruskal-Wallis test depending on the violation of normality assumption.

4.7.2. *Secondary Efficacy Analyses*

The secondary efficacy analyses will be summarized with means, standard deviations, medians and ranges for continuous variables including the changes from baseline at Week 30 in MMSE, CDR-SOB, NPI, GDS and ADCS-ADL.

These changes score from baseline at week 30 will be analyzed with Student's t-test or Kruskal-Wallis test depending on the violation of normality assumption. .

4.7.3. *Exploratory Efficacy Analyses*

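### As printed, ADAS-Cog item 13 (maze) gives a better score the sooner a subject fails, and the primary total that may contain it is undefined

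*Protocol*

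**What the plan says.** Item 13 of the ADAS-Cog form (Protocol Appendix 2, Executive Function) tells the subject to avoid dead ends and solid lines. It then records two fields:

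- Field a is the error count, which can be 0, 1 or 2.
- Field b is "Time at completion or second error", capped at 240 seconds.

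The score table has six rows, 0 to 5, and every row is a band of field b. The best row is "0-30 seconds at completion or second error", the row for 4 is "121 - 239 seconds at completion or second error", and the row for 5 is "240 seconds at completion or second error". No row mentions field a or separates a solved maze from one ended by a second error. The only other route to a 5 is the box for a task that was not administered: "Subject unable for cognitive reasons (If selected, enter a score of" 5.

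Protocol 6.1.4 makes the change in ADAS-Cog at Week 30 the primary efficacy variable. SAP 4.7.1 compares the arms "on the overall mean change from baseline to week 30 in ADAS-Cog score". Neither section lists the items in the total or gives a derivation. The form's opening instructions refer the rater to an Administration Manual that is not part of the documents.

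**The concern.** On the form's other items a higher score means worse performance. In item 3, for example, 0 is all four drawings correct and 5 is no recognisable figure. Item 13 follows that direction for solved mazes, where slower is worse. For failed mazes it reverses: the second error fixes the recorded time, so the sooner the subject fails, the better the score. A quick failure ties with the best possible performance and beats a slow, correct solution. Yet the same item gives its worst score to a subject too impaired to attempt the task.

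Appendix 2 is the only ADAS-Cog form in the protocol, and the visit sections point to it for the baseline and Week 30 assessments. If the primary total includes item 13, a subject who deteriorates from slow success to fast failure contributes an apparent gain, and the reverse course contributes an apparent loss. With 11 subjects per arm (Protocol 6.2), little averaging dilutes such a score.

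**Working it through.** The plan states no figure on this point, and Protocol 6.2 says there was no formal sample size calculation. The check is therefore to apply the printed table and compare it with a reference rule.

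**Inputs.** Score bands from Appendix 2 item 13: 0–30 s = 0, 31–60 s = 1, 61–90 s = 2, 91–120 s = 3, 121–239 s = 4, 240 s = 5. Arm size 11 from Protocol 6.2.

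**Reference rule (an assumption).** A maze ended by a second error scores 5. The documents do not state this. It is suggested by the form's own 5 for cognitive inability.

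**Step 1: misscoring of one failed maze.** Misscoring = 5 − printed score. If the subject's other visit is scored correctly, the arm mean shifts by misscoring / 11.

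| Time of second error | Printed score | Misscoring (points) | Shift in mean of 11 |
|---|---|---|---|
| 0–30 s | 0 | 5 | 5/11 = 0.45 |
| 31–60 s | 1 | 4 | 4/11 = 0.36 |
| 61–90 s | 2 | 3 | 3/11 = 0.27 |
| 91–120 s | 3 | 2 | 2/11 = 0.18 |
| 121–239 s | 4 | 1 | 1/11 = 0.09 |
| 240 s | 5 | 0 | 0 |

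**Step 2: effect on the change score.** Change = Week 30 score − baseline score, and a negative change is improvement.

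| Baseline | Week 30 | Printed change | Change under reference rule | Difference |
|---|---|---|---|---|
| solved, 200 s | second error, 20 s | 0 − 4 = −4 | 5 − 4 = +1 | −5 |
| solved, 100 s | second error, 20 s | 0 − 3 = −3 | 5 − 3 = +2 | −5 |
| second error, 20 s | solved, 100 s | 3 − 0 = +3 | 3 − 5 = −2 | +5 |
| second error, 20 s | second error, 20 s | 0 − 0 = 0 | 5 − 5 = 0 | 0 |

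The printed rule reverses the sign in the first three rows. The full 5 points requires a correctly scored visit at one end and a second error within 30 s at the other. A subject who fails in the same band at both visits has no error in the change.

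**Step 3: several subjects.** The documents do not say how often mazes are failed, so 1 to 3 affected subjects in one arm, all in the same direction, is an illustrative range. One subject shifts the arm mean by 0.09–0.45 points, two by 0.18–0.91 (2/11 to 10/11), and three by 0.27–1.36 (3/11 to 15/11).

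**Step 4: scale.** Item 13 contributes at most 5 points. The maxima of all 14 items sum to 90, and those of items 1–11 to 70, if word recall counts as 10. The documents give no standard deviation or expected effect for ADAS-Cog, so the shift cannot be set against either.

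**The case against.** The strongest reply is that the endpoint may not be touched. Both documents name only an ADAS-Cog score. If item 13 is collected but not summed, its scoring has no effect on the primary analysis. This stands as a condition on the consequence. It does not clear the form, and it shows that the total needs defining.

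Second, the Administration Manual may contain a rule for second errors. That is possible and cannot be checked here. If it does, the printed table disagrees with the manual. If it does not, the fault in the table stands. Either way the two must be reconciled.

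Third, the form is a third-party instrument used with permission, and scoring a failure as 5 is not in the documents. That is fair, so the 5 should be a default that yields to the manual.

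Fourth, the form requires a practice maze first, which may make fast failures uncommon. Their frequency is unknown in either direction.

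A reader might also infer two stronger things:

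- **That the rule favours AstroStem, or always costs 5 points.** The documents support neither. The same rule applies in both arms of a randomised, blinded comparison. The error can run either way, its size depends on the time band, and it can cancel between visits.
- **That the stray word-recall instruction in item 13 shows the item was never checked.** The line repeats one from item 12 and does not affect scoring. It says nothing about what review took place.

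**Conclusion.** The scoring fault is certain on the page: followed as printed, item 13 rewards early failure and ignores the error count recorded to identify it. This is a stated rule that gives a wrong result, not a missing detail.

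The consequence for the primary endpoint is conditional. It requires item 13 to be in the total and the form to be scored as printed, with no overriding rule in the manual. The size given in the working also assumes that a failed maze belongs in the worst category. On those assumptions the change score can be wrong in sign for an affected subject. Where the arms do not differ in how often or how fast subjects fail, this costs validity and precision without favouring either arm. The point should be corrected, but it does not show that the primary result will be biased.

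**What to change.** Before unblinding:

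1. State in SAP 4.7.1 which Appendix 2 items form the primary ADAS-Cog total.
2. Reconcile the item 13 score table with the Administration Manual. Derive the item by program from fields a and b at every visit. Apply the time bands only to mazes completed with fewer than two errors, and make sure that a maze ended by a second error cannot score better than a completed one. Use the worst category, 5, unless the manual gives another rule.
3. Report the as-printed scoring as a sensitivity analysis.
4. Remove the stray word-recall instruction from item 13.

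The cost is small. Errors and time are already recorded, so no subject needs retesting. The work is an item list and one derivation rule in the SAP, a correction to the form, and a check against the manual. The downside is a departure from the printed score table of a third-party form, which the sensitivity analysis makes visible.

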Appendix 3. MMSE (Mini-mental status examination)

Study	Protocol							
ASP1N2 AstroStem	A Phase 1/2, Randomized, Double-Blind, Placebo-Controlled Study to Evaluate the Safety and Efficacy of AstroStem, Autologous Adipose Tissue Derived Mesenchymal Stem Cells, in Patients with Alzheimer's Disease							
	Date of Assessment DD-MMM-YYYY	Time of Assessment (24-hour clock)				Assessor's Initials		
					:			
Visit Number	Subject Number				Subject Initials			

Mini-Mental State Examination (MMSE)

PAR Psychological Assessment Resources, Inc. •[name] • [name] • [name] • www.parinc.com

Adapted and reproduced by special permission of the Publisher. Psychological Assessment Resources, Inc., [name], from the Mini-Mental State Examination by Marshal Folstein and Susan Folstein, Copyright 1975, 1998, 2001 by Mini Mental LLC, Inc. Published 2001 by Psychological Assessment Resources, Inc. Further reproduction is prohibited without permission of PAR, Inc. The MMSE can be purchased from PAR by calling [contact].

ASP1N2 / MMSE 11Jan2017 Version

Adapted and reproduced by special permission of the Publisher. Psychological Assessment Resources, Inc. [name], from the Mini Mental State Examination, by Marshal Folstein and Susan Folstein, Copyright 1975, 1998, 2001 by Mini Mental LLC, Inc. Published 2001 by Psychological Assessment Resources, Inc. Further reproduction is prohibited without permission of PAR, Inc. The MMSE can be purchased from PAR, Inc. by calling [contact]

Page 1 of 6

Study	Protocol					
ASP1N2 AstroStem	A Phase 1/2, Randomized, Double-Blind, Placebo-Controlled Study to Evaluate the Safety and Efficacy of AstroStem, Autologous Adipose Tissue Derived Mesenchymal Stem Cells, in Patients with Alzheimer's Disease					
	Date of Assessment DD-MMM-YYYY	Time of Assessment (24-hour clock)				Assessor's Initials
			:			
Visit Number	Subject Number				Subject Initials	

Instructions: Words in boldface type should be read aloud clearly and slowly to the examinee. Item substitutions appear in parentheses. Administration should be conducted privately and in the examinee's primary language. Circle 0 if the response is incorrect, or 1 if the response is correct. Begin by asking the following two questions:

Do you have any trouble with your memory?	May I ask you some questions about your memory?
---	---

ORIENTATION TO TIME

What is the... year?	RESPONSE	SCORE (circle one)
season?		0 1
month of the year?		0 1
day of the week?		0 1
date?		0 1

ORIENTATION TO PLACE*

Where are you now? What is the...

state (province)?	RESPONSE	SCORE (circle one)
county (or city/town)?		0 1
city/town (or part of city/ neighborhood)?		0 1
building (name of type)?		0 1
floor of the building (room number or address)?		0 1

*Alternative place words that are appropriate for the setting and increasingly precise may be substituted and noted.

REGISTRATION*

Listen carefully. I am going to say three words. You say them back after I stop. Ready?

Here they are...APPLE [pause], PENNY [pause], TABLE [pause]. Now repeat those words back to me.

[Repeat up to 5 times, but score only the first trial.]

APPLE	RESPONSE	SCORE (circle one)
PENNY		0 1
TABLE		0 1

Now keep those words in mind. I am going to ask you to say them again in a few minutes.

*Alternative word sets (e.g., PONY, QUARTER, ORANGE) may be substituted and noted when retesting an examinee.

ATTENTION AND CALCULATION [Serial 7s]*

Now I'd like you to subtract 7 from 100. Then keep subtracting 7 from each answer until I tell you to stop.

What is 100 take away 7? If needed, say: Keep going.	[93] [86]	RESPONSE	SCORE (circle one)
If needed, say: Keep going.	[79]		0 1
If needed, say: Keep going.	[72]		0 1
If needed, say: Keep going.	[65]		0 1

*Alternative item (WORLD backward) should only be administered if the examinee refuses to perform the Serial 7s task →

Substitute and score this item only if the examinee refuses to perform the Serial 7s task.

Spell WORLD forward, then backward.

Correct forward spelling if misspelled.

But score only the backward spelling.

(D = 1) (L = 1) (R = 1) (O = 1) (W = 1) (0 to 5)

RECALL

What were those three words I asked you to remember? [Do not offer any hints.]

	RESPONSE	SCORE (circle one)
APPLE	<hr/>	0 1
PENNY	<hr/>	0 1
TABLE	<hr/>	0 1

NAMING*

What is this? [Point to a pencil or pen.]

What is this? [Point to a watch.]

*Alternative common objects (e.g., eyeglasses, chair, keys) may be substituted and noted.

<hr/>	0 1
<hr/>	0 1

REPETITION

Now I am going to ask you to repeat what I say. Ready? "NO IFS, ANDS, OR BUTS." Now you say that.
[Repeat up to 5 times, but score only the first trial.]

NO IFS, ANDS, OR BUTS.

 0 1

Detach the next page along the lengthwise perforation, and then tear it in half along the horizontal perforation. Use the upper half of the page (blank) for the Comprehension, Writing, and Drawing items that follow. Use the lower half of the page as a stimulus form for the Reading ("CLOSE YOUR EYES") and Drawing (intersecting pentagons) items.

COMPREHENSION

Listen carefully because I am going to ask you to do something.

Take this paper in your right hand [pause], fold it in half [pause], and put it on the floor (or table).

TAKE IN RIGHT HAND	_____	0	1
FOLD IN HALF	_____	0	1
PUT ON FLOOR (or TABLE)	_____	0	1

READING

Please read this and do what it says. [Show examinee the words on the stimulus form.]

CLOSE YOUR EYES	_____	0	1
-----------------	-------	---	---

WRITING

Please write a sentence. [If examinee does not respond, say: Write about the weather.]

Place the blank piece of paper (unfolded) in front of the examinee and provide a pen or pencil. Score 1 point if the sentence is comprehensible and contains a subject and a verb. Ignore errors in grammar or spelling.

0 1

DRAWING

Please copy this design. [Display the intersecting pentagons on the stimulus form.]

[figure not shown]
Score 1 point if the drawing consists of two 5-sided figures that intersect to form a 4-sided figure.

0 1

Assessment of level of consciousness.

Alert/ Responsive	Drowsy	Stuporous	Comatose/ Unresponsive	Total Score = (sum all item scores.)	(30 points max.)
----------------------	--------	-----------	---------------------------	---	------------------

CLOSE YOUR EYES

Appendix 4. CDR-SOB (Clinical Dementia Rating-Sum of Box)

Study	A Phase 1/2, Randomized, Double-Blind, Placebo-Controlled Study to Evaluate the Safety and Efficacy of AstroStem, Autologous Adipose Tissue Derived Mesenchymal Stem Cells, in Patients with Alzheimer's Disease												Protocol
ASP1N2 AstroStem													AST-ADP2-US01
	Date of Assessment DD-MMM-YYYY						Time of Assessment (24-hour clock)						Assessor's Initials
Visit Number	Subject Number						Subject Initials						Caregiver Initials

Clinical Dementia Rating Worksheet

This is a semi-structured interview. Please ask all of these questions. Ask any additional questions necessary to determine the subject's CDR. Please note information from the additional questions.

Memory Questions for Informant:

1. Does he/she have a problem with his/her memory or thinking? Yes No
- 1a. If yes, is this a consistent problem (as opposed to inconsistent)? Yes No
2. Can he/she recall recent events? Usually Sometimes Rarely
3. Can he/she remember a short list of items (shopping)? Usually Sometimes Rarely
4. Has there been some decline in memory during the past year? Yes No
5. Is his/her memory impaired to such a degree that it would have interfered with his/her activities of daily life a few years ago (or pre-retirement activities)? (collateral sources opinion) Yes No
6. Does he/she completely forget a major event (e.g., trip, party, family wedding) within a few weeks of the event? Usually Sometimes Rarely
7. Does he/she forget pertinent details of the major event? Usually Sometimes Rarely
8. Does he/she completely forget important information of the distant past (e.g., birthdate, wedding date, place of employment)? Usually Sometimes Rarely
9. Tell me about some recent event in his/her life that he/she should remember. (For later testing, obtain details such as location of the event, time of day, participants, how long the event was, when it ended and how the subject or other participants got there).
Within 1 week : _____

Within 1 month: _____

10. When was he/she born? _____
11. Where was he/she born? _____
12. What was the last school he/she attended? _____
Name _____
Place _____
Grade _____
13. What was his/her main occupation/job (or spouse's job if subject was not employed)? _____
14. What was his/her last major job (or spouse's job if subject was not employed)? _____
15. When did he/she (or spouse) retire and why? _____

Reprinted with permission. The Clinical Dementia Rating (CDR) is a copyrighted instrument of the Alzheimer's Disease Research Center, Washington University, St. Louis, Missouri, USA. All rights reserved.

ASP1N2 / CDR v2.0 2Nov2017

Page 1 of 11

Clinical Dementia Rating Worksheet

Orientation Questions for Informant:

How often does he/she know of the exact:

1. Date of the Month?

Usually Sometimes Rarely Don't Know

2. Month?

Usually Sometimes Rarely Don't Know

3. Year?

Usually Sometimes Rarely Don't Know

4. Day of the Week?

Usually Sometimes Rarely Don't Know

5. Does he/she have difficulty with time relationships (when events happened in relation to each other)?

Usually Sometimes Rarely Don't Know

6. Can he/she find his/her way about familiar streets?

Usually Sometimes Rarely Don't Know

7. How often does he/she know how to get from one place to another outside his/her neighborhood?

Usually Sometimes Rarely Don't Know

8. How often can he/she find his/her way about indoors?

Usually Sometimes Rarely Don't Know

Reprinted with permission. The Clinical Dementia Rating (CDR) is a copyrighted instrument of the Alzheimer's Disease Research Center, Washington University, St. Louis, Missouri, USA. All rights reserved.

ASP1N2 / CDR v2.0 2Nov2017

Page 2 of 11

Clinical Dementia Rating Worksheet

Judgment and Problem Solving Questions for Informant:

1. In general, if you had to rate his/her abilities to solve problems at the present time, would you consider them:
 As good as they have ever been
 Good, but not as good as before
 Fair
 Poor
 No ability at all
2. Rate his/her ability to cope with small sums of money (e.g., make change, leave a small tip):
 No loss
 Some loss
 Severe loss
3. Rate his/her ability to handle complicated financial or business transaction (e.g., balance check-book, pay bills):
 No loss
 Some loss
 Severe loss
4. Can he/she handle a household emergency (e.g., plumbing leak, small fire)?
 As well as before
 Worse than before because of trouble thinking
 Worse than before, another reason (why) _____

5. Can he/she understand situations or explanations?
 Usually Sometimes Rarely Don't Know
6. Does he/she behave* appropriately [i.e., in his/her usual (premorbid) manner] in social situations and interactions with other people?
 Usually Sometimes Rarely Don't Know

*This item rates behavior, not appearance.

Clinical Dementia Rating Worksheet

Community Affairs Questions for Informant: Occupational

1. Is the subject still working? Yes No N/A
If not applicable, proceed to item 4
If yes, proceed to item 3
If no, proceed to item 2

2. Did memory or thinking problem contribute to the subject's decision to retire? Yes No D/K
(Question 4 is next)

3. Does the subject have significant difficulty in his/her job because of problems with memory or thinking?
 Rarely or Never Sometimes Usually Don't Know

Social

4. Did he/she ever drive a car? Yes No
Does the subject drive a car now? Yes No
If no, is this because of memory or thinking problems? Yes No

5. If he/she is still driving, are there problems or risks because of poor thinking? Yes No

*6. Is he/she able to independently shop for needs?
 Rarely or Never Sometimes Usually Don't Know
(Needs to be accompanied on any shopping trip) (Shops for limited number of items: buys duplicate items or forgets needed items)

7. Is he/she able to independently carry out activities outside the home?
 Rarely or Never Sometimes Usually Don't Know
(Generally unable to perform activities without help) (Limited and/or routine, e.g., superficial participation in church or meetings: trips to beauty parlor) (Meaningful participation in activities, e.g., voting)

8. Is he/she taken to social functions outside a family home? Yes No
If no, why not? _____

9. Would a casual observer of the subject's behavior think the subject was ill? Yes No

10. If in nursing home, does he/she participate well in social functions (thinking)? Yes No

IMPORTANT:

Is there enough information available to rate the subject's level of impairment in community affairs?

If not, please probe further.

Community Affairs: Such as going to church, visiting with friends or family, political activities, professional organizations such as bar association, other professional groups social clubs, service organization, educational programs.

*Please add notes if needed to clarify subject's level of functioning in this area.

Home and Hobbies Questions for Informant:

1a. What changes have occurred in his/her abilities to perform household chores? _____

1b. What can he/she still do well? _____

2a. What changes have occurred in his/her abilities to perform hobbies? _____

2b. What can he/she still do well? _____

3. If in nursing home, what can he/she no longer do well (H and H)?

Everyday Activities (Blessed):

IMPORTANT:

Is there enough information available to rate the subject's level of impairment in HOME & HOBBIES?
If not, please probe further.

Homemaking Tasks: Such as cooking, laundry, cleaning, grocery shopping, taking out garbage, yard work, simple care maintenance, and basic home repair.

Hobbies: Sewing, painting, handicrafts, reading, entertaining, photography, gardening, going to theater or symphony, woodworking, participation in sports.

Reprinted with permission. The Clinical Dementia Rating (CDR) is a copyrighted instrument of the Alzheimer's Disease Research Center, Washington University, St. Louis, Missouri, USA. All rights reserved.

ASPIRE, CDR VERSUS CDR17

Page 5 of 11

Clinical Dementia Rating Worksheet

Personal Care Questions for Informant:

*What is your estimate of his/her mental ability in the following areas:

	Unaided	Occasionally misplaced buttons, etc.	Wrong sequence commonly forgotten items	Unable to dress
A. Dressing (Blessed)	0	1	2	3
	Unaided	Needs prompting	Sometimes needs help	Always or nearly always needs help
B. Washing, grooming	0	1	2	3
	Cleanly: proper utensils	Messily: spoon	Simple solids	Has to be fed completely
C. Eating habits	0	1	2	3
	Normal complete control	Occasionally wets bed	Frequently wets bed	Doubly incontinent
D. Sphincter control (Blessed)	0	1	2	3

*A box-score of 1 can be considered if the subject's personal care is impaired from a previous level, even if they do not receive prompting.

Clinical Dementia Rating Worksheet

Memory Questions for Subject:

1. Do you have problems with memory or thinking? Yes No
2. A few moments ago your (spouse, etc.) told me a few recent experiences you had. Will you tell me something about those? (Prompt for details, if needed such as location of the event, time of day, participants, how long the event was, when it ended and how the subject or other participants got there).

Within 1 week

1.0 – Largely correct _____

0.5 _____

0.0 – Largely incorrect _____

Within 1 month

1.0 – Largely correct _____

0.5 _____

0.0 – Largely incorrect _____

3. I will give you a name and address to remember for a few minutes. Repeat this name and address after me: (Repeat until the phrase is correctly repeated or to a maximum of three trials).

Elements	1	2	3	4	5
	John	Brown,	42	Market Street,	Chicago
	John	Brown,	42	Market Street,	Chicago
	John	Brown,	42	Market Street,	Chicago

(Underline elements repeated correctly in each trial).

4. When were you born? _____

5. Where were you born? _____

6. What was the last school you attended?

Name _____

Place _____ Grade _____

7. What was your main occupation job (or spouse if not employed)? _____

8. What was your last major job (or spouse if not employed)? _____

9. When did you (or spouse) retire and why? _____

10. Repeat the name and address I asked you to remember:

Elements	1	2	3	4	5
	John	Brown,	42	Market Street,	Chicago

(Underline elements repeated correctly).

Clinical Dementia Rating Worksheet

Orientation Question for Subject:

Record the subject's answer verbatim for each question

1. What is the date today?

Correct Incorrect

2. What day of the week is it?

Correct Incorrect

3. What is the month?

Correct Incorrect

4. What is the year?

Correct Incorrect

5. What is the name of this place?

Correct Incorrect

6. What town or city are we in?

Correct Incorrect

7. What time is it?

Correct Incorrect

8. Does the subject know who the informant is (in your judgment)?

Correct Incorrect

Reprinted with permission. The Clinical Dementia Rating (CDR) is a copyrighted instrument of the Alzheimer's Disease Research Center, Washington University, St. Louis, Missouri, USA. All rights reserved.

ASP1N2 / CDR v2.0 2Nov2017

Page 8 of 11

Clinical Dementia Rating Worksheet

Judgment and Problem Solving Question for Subject:

Instructions: If initial response by subject does not merit a grade 0, press the matter to identify the subject's best understanding of the problem. Circle nearest response.

Similarities:

Example: "How are a pencil and pen alike? (writing instruments)

How are these things alike?"	Subject's Response
1. turnip cauliflower	_____
(0 = vegetables)	
(1 = edible food, living things, can be cooked, etc.)	
(2 = answers not pertinent; differences; buy them)	
2. desk bookcase	_____
(0 = furniture, office furniture; both hold books)	
(1 = wooden, legs)	
(2 = not pertinent, differences)	

Differences:

Example: "What is the difference between sugar and vinegar? (sweet vs. sour)

What is the difference between these things?"

3. lie mistake	_____
(0 = one deliberate, one unintentional)	
(1 = one bad the other good – or explains only one)	
(2 = anything else, similarities)	
4. river canal	_____
(0 = natural – artificial)	
(2 = anything else)	

Calculations:

5. How many nickels in a dollar?	 Correct	 Incorrect
6. How many quarters in \$6.75?	 Correct	 Incorrect
7. Subtract 3 from 20 and keep subtracting 3 from each new number all the way down.	 Correct	 Incorrect

Judgment:

8. Upon arriving in a strange city, how would you locate a friend that you wished to see?
(0 = try the telephone book, go to the courthouse for a directory; call a mutual friend)
(1 = call the police, call operator (usually will not give address))
(2 = no clear response)

9. Subject's assessment of disability and station in life and understanding of why he/she is present at the examination (may have covered, but rate here):

Good Insight Partial Insight Little Insight

Reprinted with permission. The Clinical Dementia Rating (CDR) is a copyrighted instrument of the Alzheimer's Disease Research Center, Washington University, St. Louis, Missouri, USA. All rights reserved.

ASP1N2 / CDR v2.0 2Nov2017

Page 9 of 11

Clinical Dementia Rating (CDR)

CLINICAL DEMENTIA RATING (CDR)	0	0.5	1	2	3
--------------------------------	---	-----	---	---	---

		Impairment				
		None 0	Questionable 0.5	Mild 1	Moderate 2	Severe 3
Memory	No memory loss or slight inconsistent forgetfulness	Consistent slight forgetfulness; partial recollection of events; "benign" forgetfulness	Moderately marked for recent events; defect interferes with everyday activities	Severe memory loss; only highly learned material retained; new material rapidly lost	Severe memory loss; only fragment remain	
	Fully oriented	Fully oriented except for slight difficulty with time relationships	Moderately difficult with time relationships; oriented for place at examination; may have geographic disorientation elsewhere	Severe difficulty with time relationships; usually disoriented to time, often to place	Oriented to person only	
Orientation	Solves everyday problems & handles business & financial affairs well; judgment good in relation to past performance	Slight impairment in solving problems, similarities, and differences	Moderately difficult in handling problems, similarities, and differences; social judgment usually maintained	Severely impaired in handling problems, similarities, and differences; social judgment usually impaired	Unable to make judgments or solve problems	
	Independent function at usual level in job, shopping, volunteer and social groups	Slight impairment in these activities	Unable to function independently at these activities although may still be engaged in some; appears normal to casual inspection	No pretense of independent function outside home		
Community Affairs	Life at home, hobbies, and intellectual interests well maintained	Life at home, hobbies, and intellectual interests slightly impaired	Mild but definite impairment of function at home; more difficult chores abandoned; more complicated hobbies and interests abandoned	Appears well enough to be taken to functions outside a family home	Appears too ill to be taken to functions outside a family home	
	Fully capable of self-care	Needs prompting	Requires assistance in dressing, hygiene, keeping of personal effects	Requires much help with personal care; frequent incontinence		
Personal Care						

Score only as decline from previous usual level due to cognitive loss, not impairment due to other factors.

Reprinted with permission. The Clinical Dementia Rating (CDR) is a copyrighted instrument of the Alzheimer's Disease Research Center, Washington University, St. Louis, Missouri, USA.
All rights reserved.
ASP1N2 / CDR v2.0 2Nov2017

Study	Protocol									
ASP1N2 AstroStem	A Phase 1/2, Randomized, Double-Blind, Placebo-Controlled Study to Evaluate the Safety and Efficacy of AstroStem, Autologous Adipose Tissue Derived Mesenchymal Stem Cells, in Patients with Alzheimer's Disease									
	Date of Assessment DD-MMM-YYYY					Time of Assessment (24-hour clock)				Assessor's Initials
							:			
Visit Number						Subject Number			Subject Initials	

Clinical Dementia Rating

Score only as decline from previous usual level due to cognitive loss, not impairment due to other factors.

Categories	Score
Memory	
Orientation	
Judgement & Problem Solving	
Community Affairs	
Home & Hobbies	
Personal Care	
CDR Sum of Boxes Score	

Reprinted with permission. The Clinical Dementia Rating (CDR) is a copyrighted instrument of the Alzheimer's Disease Research Center, Washington University, St. Louis, Missouri, USA. All rights reserved.
ASP1N2 / CDR v2.0 2Nov2017

Page 11 of 11

